9.2.4 Regulatory Reporting Requirements for SAEs

- Prompt notification by the investigator to the Sponsor of SAEs is essential so that legal obligations and ethical responsibilities towards the safety of participants and the safety of a product under clinical investigation are met.
- An investigator who receives an investigator safety report describing SAEs or other specific safety information (eg, summary or listing of SAEs) from the Sponsor will file it along with the IB and will notify the IRB/IEC, if appropriate according to local requirements.

Sponsor or designee will be reporting adverse events to regulatory authorities and ethics committees according to local applicable laws including European Directive 2001/20/EC and FDA Code of Federal Regulations 21 CFR Parts 312 and 320. A SUSAR (Suspected, Unexpected Serious Adverse Reaction) is a subset of SAEs and will be reported to the appropriate regulatory authorities and investigators following local and global guidelines and requirements.

9.2.6 Pregnancy

In the event a **participant** becomes pregnant during the trial, the study treatment must be discontinued immediately. If the **participant** becomes pregnant during the study period until the end of study, the investigator must immediately notify the Clinical Trial Physician/Medical Monitor/designee of this event and complete and forward a Pregnancy Surveillance Form to BMS Designee within 24 hours of awareness of the event and in accordance with SAE reporting procedures described in [Appendix 3](#).

Follow-up information regarding the course of the pregnancy, including perinatal and neonatal outcome and, where applicable, offspring information must be reported on the Pregnancy Surveillance Form.

In all cases, the study treatment will be permanently discontinued.

Any pregnancy that occurs in a female partner of a male study participant should be reported to BMS Drug Safety. For the Sponsor or designee to collect any pregnancy surveillance information from the female partner, the female partner must sign an ICF for disclosure of this information. Information on this pregnancy will be collected on the Pregnancy Surveillance Form.

Protocol-required procedures for study discontinuation and follow-up must be performed on the participant.

Follow-up information regarding the course of the pregnancy, including perinatal and neonatal outcome and, where applicable, offspring information must be reported on the Pregnancy Surveillance Form.

9.2.7 *Laboratory Test Result Abnormalities*

The following laboratory test result abnormalities should be captured on the nonserious AE CRF page or SAE Report Form electronic, as appropriate. Paper forms are only intended as a back-up option when the electronic system is not functioning.

- Any laboratory test result that is clinically significant or meets the definition of an SAE.
- Any laboratory test result abnormality that required the participant to have study treatment discontinued or interrupted.
- Any laboratory test result abnormality that required the participant to receive specific corrective therapy.

It is expected that wherever possible, the clinical rather than laboratory term would be used by the reporting investigator (eg, anemia versus low hemoglobin value).

9.2.8 *Potential Drug Induced Liver Injury (DILI)*

Wherever possible, timely confirmation of initial liver-related laboratory abnormalities should occur prior to the reporting of a potential DILI event. All occurrences of potential DILIs, meeting the defined criteria, must be reported as SAEs (see [Section 9.2](#) and [Appendix 3](#) for reporting details).

Potential drug induced liver injury is defined as:

- AT (ALT or AST) elevation $> 3 \times$ ULN
 - AND -
- Total bilirubin $> 2 \times$ ULN, without initial findings of cholestasis (elevated serum alkaline phosphatase),
 - AND -
- No other immediately apparent possible causes of AT elevation and hyperbilirubinemia, including, but not limited to, viral hepatitis, pre-existing chronic or acute liver disease, or the administration of other drug(s) known to be hepatotoxic.

9.2.9 Other Safety Considerations

Any significant worsening noted during interim or final physical examinations, electrocardiogram, x-ray filming, any other potential safety assessment required or not required by protocol should also be recorded as a nonserious or serious AE, as appropriate, and reported accordingly.

9.3 Overdose

For this study, any dose of deucravacitinib greater than 24 mg within a 24-hour time period will be considered an overdose. However, if a participant takes a higher dose than assigned (even if < 24 mg in a 24-hour period), this deviation should be documented appropriately.

In the event of an overdose, the investigator should carry out all of the following actions:

- 1) Contact Clinical Trial Physician/Medical Monitor immediately.
- 2) Closely monitor the participant for AEs, SAEs, and laboratory abnormalities until BMS-986165 can no longer be detected systemically (at least 3 days).
- 3) Obtain a plasma sample [REDACTED] within 3 days from the date of the last dose of study treatment if requested by the Clinical Trial Physician/Medical Monitor (determined on a case-by-case basis).
- 4) Document the quantity of the excess dose as well as the duration of the overdosing in the CRF.

9.4 Safety

Planned time points for all safety assessments are listed in the Schedule of Activities ([Section 2](#)).

All urgent safety concerns must be discussed with the Sponsor immediately upon occurrence or awareness to determine if the participant should continue or discontinue treatment. Safety evaluations that will be performed in addition to AE monitoring are physical examinations ([Section 9.4.1](#)), TB screening ([Section 9.4.2](#)), vital signs, ECGs, concomitant medication use, and laboratory tests ([Section 9.4.5](#)).

9.4.1 Physical Examinations

Schedules for physical examinations are provided in [Section 2](#). Complete and/or targeted PEs may be performed by a Doctor of Medicine (MD), or someone who is authorized to perform the examinations by training and has been delegated this task by the principal investigator. While the targeted examination may not be as comprehensive as the initial full examination, key aspects should evaluate important body systems as clinically indicated. These body systems can include lymph nodes, liver, spleen, and breast at the discretion of the examiner. A targeted examination may note any changes in the participant's condition (body systems) since the last assessment and does not preclude examination of any of the other body systems as clinically indicated. Every effort should be made to ensure the same evaluator will complete the examination for each participant at all visits throughout the study. Documentation of who performed the examination is to be recorded in source notes.

9.4.2 *Tuberculosis Screening and Chest X-ray*

A chest X-ray and PE are part of the process to assess a participant's eligibility as defined in [Section 6.2, Exclusion Criteria, 6\) a\)](#), and outlined in [Section 2](#). A chest X-ray at the Screening Visit is required if not already performed within 6 months of obtaining written informed consent.

In addition to a complete PE and medical history to evaluate exposure to TB, all participants will have a screening test, an IGRA (eg, T-spot® or QuantiFERON®), preferably performed centrally. If unable to obtain central laboratory results (eg, repeated test due to indeterminate result), an IGRA test could be obtained locally, after consultation with the Clinical Trial Physician/Medical Monitor.

9.4.3 *Vital signs*

Refer to Schedule of Activities in Section 2.

9.4.4 *Electrocardiograms*

Refer to Schedule of Activities in Section 2.

9.4.5 *Clinical Safety Laboratory Assessments*

A central laboratory will perform assessments of safety laboratory assessments (except pregnancy tests) and provide reference ranges and laboratory reports. Investigators must document their review of each laboratory safety report. Any laboratory test result that the investigator considers clinically relevant is to be recorded on the appropriate AE page of the CRF ([Section 9.2.7](#)). Results of clinical laboratory tests performed during screening must be available prior to randomization.

The laboratory parameters to be assessed are as follows:

[figure not shown]
- Hematology: hemoglobin, hematocrit, total leukocyte count (including differential), platelet count, red blood cell count, and manual differential (separate smear).
- Chemistry: AST, ALT, gamma glutamyltransferase, total bilirubin, direct bilirubin, alkaline phosphatase, lactate dehydrogenase, creatinine, blood urea nitrogen, uric acid, [REDACTED] glucose, total protein, albumin, sodium, potassium, chloride, calcium, phosphorus, magnesium, creatine kinase, creatinine clearance (Screening only).
- Coagulation (Screening only): prothrombin time, international normalized ratio, and either partial thromboplastin time or activated partial thromboplastin time.
- Lipid Panels (Placebo-controlled and Active Treatment Only) tests performed [REDACTED] [REDACTED]: lipid panel (total cholesterol, high-density lipoprotein cholesterol, low-density lipoprotein cholesterol, and triglycerides).
- Urinalysis: protein, glucose, blood, leukocyte esterase, specific gravity, pH; microscopic examination of the sediment if blood, protein, or leukocyte esterase are positive on dipstick; spot urine will be assessed for urine protein and urine creatinine.
- Serology to be performed at screening: Hepatitis C antibody, anti-HBs, HBsAg, anti-HBc, HIV-1 and HIV-2 antibody.
- TB (screening only).

[figure not shown]
- C3, C4, Anti-dsDNA: At Screening for all participants, and subsequent collections only for participants with antibodies elevated above normal at Screening.

[figure not shown]
In addition, urine pregnancy testing will be performed for WOCBP, and follicle-stimulating hormone will be measured to confirm postmenopausal status (as applicable; at screening only). Additional safety assessments may be performed at local laboratories at the investigator's discretion.

9.4.6 *Imaging Safety Assessment*

Not applicable.

9.9

Health Economics OR Medical Resource Utilization and Health Economics

Health Economics/Medical Resource Utilization and Health Economics parameters will not be evaluated in this study.

10

STATISTICAL CONSIDERATIONS

10.2 Populations for Analyses

For purposes of analysis, the following populations are defined:

Population	Description
Enrolled	All participants who sign informed consent.
Randomized	All participants who are randomized to a treatment. Participants will be grouped according to the treatment to which they are randomized according to IRT at the start of the treatment period.
As Treated	
All participants who took at least 1 dose of double blind study treatment in the placebo-controlled part of the study.
 
The treatment group “as treated” will be the same as the treatment group “as randomized” by IRT, except in the following cases:
 
• If a participant took the same incorrect treatment throughout the study, then the participant will be analyzed based on the treatment received.• If a participant took study drug from more than one treatment group, and none of the administrations were consistent with the assigned randomized treatment group, then the participant will be analyzed based on the first treatment taken.
As-Treated (Active Treatment Period)	
All randomized participants who took at least 1 dose of double-blind study treatment in the active treatment period. Participants will be included in the treatment path they were randomized, except in the following cases:
 
• If a participant took the same incorrect treatment throughout a respective treatment period, then the participant will be analyzed based on the treatment received in each treatment period.• If a participant took study drug from more than one treatment group within a treatment period, and none of the administrations were consistent with the assigned randomized treatment group, then the participant will be analyzed based on the first treatment taken within each treatment period. 
Participants will be grouped according to the following treatment sequences:
 
• Deucravacitinib 3 mg BID □ deucravacitinib 3 mg BID• Deucravacitinib 6 mg BID □ deucravacitinib 6 mg BID• Placebo □ deucravacitinib 3 mg BID
- OR -• Placebo □ deucravacitinib 6 mg BID.

Abbreviations: BID = twice a day; IRT = Interactive Response Technology.

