5.1.3 Active Treatment Period (Week 16 to Week 52)

Participants who complete the placebo-controlled treatment period will continue into an active treatment period for an additional 36 weeks of treatment.

At Week 16, participants receiving placebo during the placebo-controlled treatment period will be re-randomized 1:1 in a blinded-fashion to receive active treatment with either deucravacitinib 3 mg BID or 6 mg BID until Week 52. Participants receiving deucravacitinib 3 mg BID or 6 mg BID through Week 16 will continue on the originally randomized treatment in a blinded manner through Week 52 (Table 2-3).

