5.2 Number of Participants

Approximately 75 participants will be randomized in a 1:1:1 ratio to receive deucravacitinib 3 mg BID, deucravacitinib 6 mg BID, or deucravacitinib-matching Placebo BID. Sample size considerations are described [REDACTED].

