10.3.2 Safety Analyses

All safety analyses will be performed on the As-treated analysis population.

Endpoint	Statistical Analysis Methods
Primary	Not applicable as all safety assessments and variables are considered secondary.
Secondary	Safety assessments and variables during the 16-week placebo-controlled treatment period (TP), as specified in Table 4-1 , will be summarized descriptively by treatment group (combined BMS doses, each BMS dose, and placebo). Adverse events will be listed and tabulated by System Organ Class (SOC) and Preferred Term (PT). Categorical data will be summarized as frequency counts and percentages. Continuous data for absolute and change from baseline values will be summarized using n, mean, standard deviation, median, minimum, and maximum, unless otherwise specified.

Abbreviations: n = number of samples; PT = Preferred Term; SOC = System Organ Class; TP = treatment period.

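### The As Treated regrouping rule is not limited to the placebo-controlled period, so a participant misdosed for all of Weeks 0–16 can stay in the wrong column of the 16-week safety tables

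*Combined protocol and SAP*

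**What the plan says.** The table in protocol Section 10.2 has two rows for treated participants.

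- **As Treated.** A participant enters by having taken study drug in the placebo-controlled part: "took at least 1 dose of double blind study treatment in the placebo-controlled part of the study". The participant is grouped as randomized, with two exceptions. Exception 1: "If a participant took the same incorrect treatment throughout the study, then the participant will be analyzed based on the treatment received". Exception 2 begins "If a participant took study drug from more than one treatment group, and none of the administrations were consistent with the assigned randomized treatment group" and sends the participant to the first treatment taken. Exception 2 states no period.
- **As-Treated (Active Treatment Period).** The parallel exceptions here work by period. The first begins "If a participant took the same incorrect treatment throughout a respective treatment period", and the second refers to drug taken within a treatment period.

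Section 10.3.2 bases all safety analyses on the As-treated population. It summarizes safety over the 16-week placebo-controlled period in columns for each dose, both doses combined, and placebo. Under Section 5.1.3, participants on 3 mg or 6 mg "will continue on the originally randomized treatment in a blinded manner through Week 52", while placebo participants are re-randomized to one of the two doses at Week 16.

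**The concern.** The population and the tables it serves concern Weeks 0–16, but the test for regrouping looks at dosing over the whole study. A participant in the 3 mg or 6 mg arm keeps the same assignment to Week 52. Correct doses after Week 16 can therefore cancel a regrouping that Weeks 0–16 alone would require. Adverse events from Weeks 0–16, or their absence, would then be reported under a treatment the participant did not take in that period, because of doses taken after the period being tabulated.

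There is also a conditional point. Section 7.3 mentions a database lock whose name is blacked out, separately from the final lock. If the 16-week tables are produced at an earlier lock, a rule that depends on later dosing could place the same participant in different columns at the two locks.

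**Working it through.** The plan gives no figure to reproduce. The check applies the rules as written to every relevant dosing path and then sizes the effect of one misplaced participant.

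**1. The basic case.** Take a participant randomized to 3 mg who took 6 mg for all of Weeks 0–16 and 3 mg afterwards.

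- Exception 1 fails, because the wrong drug was not taken for the whole study.
- Exception 2 fails, because the later doses match the assignment.
- The default applies, and the participant is tabulated under 3 mg.
- If both exceptions are limited to Weeks 0–16, exception 1 applies and the participant is tabulated under 6 mg.

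**2. All paths with no correct dose in Weeks 0–16.** The assignment is judged against the original randomization. After Week 16 the participant either takes the assigned (or re-randomized) drug or has already stopped.

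| Weeks 0–16 | After Week 16 | Paths | Kept as randomized, literal rule | Kept as randomized, rule limited to Weeks 0–16 |
|---|---|---|---|---|
| Same wrong treatment | Assigned or re-randomized drug | 8 | 4 | 0 |
| Two different wrong treatments | Assigned or re-randomized drug | 8 | 4 | 0 |
| Same wrong treatment | Stopped | 6 | 0 | 0 |
| Two different wrong treatments | Stopped | 6 | 0 | 0 |
| Total | | 28 | 8 | 0 |

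All 8 retained paths belong to the 3 mg and 6 mg arms. For a single wrong treatment they are 3 mg arm on 6 mg, 3 mg arm on placebo, 6 mg arm on 3 mg, and 6 mg arm on placebo. Placebo-randomized participants who took active drug never take placebo later, so one of the exceptions regroups them. Participants who stop before the active period are regrouped if the study is taken to mean their own dosing. These are counts of logical paths and say nothing about frequency.

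**3. Size for one misplaced participant who has the event.** Section 5.2 states "Approximately 75 participants will be randomized in a 1:1:1 ratio", so 75/3 = 25 per arm. Let k be the events tabulated in the randomized arm or combined group, with this participant counted, and m those tabulated in the arm actually received, with this participant left out.

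| Column | Formula | Ceiling | At an assumed 20% event rate |
|---|---|---|---|
| Randomized arm | k/25 − (k−1)/24 | k=1: 1/25 − 0/24 = 4.0 points | k=5: 5/25 − 4/24 = 3.3 points |
| Arm received | (m+1)/26 − m/25 | m=0: 1/26 − 0/25 = 3.8 points | m=5: 6/26 − 5/25 = 3.1 points |
| Combined active | k/50 − (k−1)/49 | k=1: 1/50 − 0/49 = 2.0 points | k=10: 10/50 − 9/49 = 1.6 points |

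The combined column changes only when the wrong treatment was placebo. The 20% rate is an assumption for illustration, because the protocol gives no expected event rate.

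**The case against.** The best defence is that the study, in exception 1, was meant as the placebo-controlled part. The population is defined by dosing in that part, a separate row covers the active period, and that row shows the sponsor groups by period. This reading is possible. Against it, the entry condition in the same cell names the placebo-controlled part as a portion of the study, and the next row shows that period wording was at hand. If the narrower meaning was intended, the text is ambiguous and the same edit settles it.

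The active-period row does not close the gap, because it governs a different population. It would classify the participant in step 1 by the treatment received in each period, as 6 mg then 3 mg. That sequence is not among the four listed, and it would disagree with the As Treated row about Weeks 0–16.

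Three further points stand.

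- **Rarity.** Drug is assigned centrally and dispensed at Day 1 and Weeks 4, 8, 12 and 16. The main case needs the same wrong drug at four consecutive dispensings and the right drug from Week 16. A systematic assignment error would more likely persist, and exception 1 already handles that.
- **Partial misdosing.** A participant with even one correct administration in Weeks 0–16 still stays as randomized after the edit. That is the protocol's convention and is not at issue here.
- **The SAP.** Section 10.3 leaves the selection of participants to a SAP, and the supplied document contains no SAP text on this rule. The grouping may be clarified there.

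It is also fair that, in exception 2 of the active-period row, the period limit is attached to taking drug from more than one group and not to the clause about no administration matching the assignment. Copying that phrase in the same position might not be enough.

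**Conclusion.** The concern holds. As written, the As Treated rule keeps a 3 mg or 6 mg participant in the randomized column of the 16-week safety tables when every dose in that period was wrong and later doses were right. This rests on the literal meaning of the whole-study wording and on judging the assignment against the original randomization.

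The impact is very small. One such participant with an event shifts a single arm by no more than 4.0 points and the combined active group by no more than 2.0, assuming 25 treated participants per arm. The safety comparison is descriptive, and the efficacy analyses in Section 10.3.1 use the randomized population and are unaffected. The correction is desirable but not essential.

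**What to change.** In the As Treated row of Section 10.2, end the condition in exception 1 with *throughout the placebo-controlled treatment period* in place of the whole-study wording. In exception 2, add *within the placebo-controlled treatment period*, placed so that it governs both the mixed-treatment condition and the condition that no administration matched the assignment. Carry the same wording into the SAP before database lock.

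The cost is one phrase in each of two bullets. No data collection, sample size or clinical procedure changes.

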10.3 Statistical Analyses

The statistical analysis plan (SAP) will be developed and finalized before database lock and will describe the selection of participants to be included in the analyses, and procedures for accounting for missing, unused, and spurious data. Below is a summary of planned statistical analyses of the primary and secondary endpoints. See [Table 4-1](#) for the list of endpoints.

A description of the participant population will be included in a statistical output report, including subgroups of age, gender and race.

10.3.1 Efficacy Analyses

Endpoint	Statistical Analysis Methods
Primary	
Percent change from baseline over time for CLASI-A score will be analyzed using a longitudinal repeated measures analysis on the randomized population.
 
[REDACTED]
 
Adjusted mean % changes (LSMEANS) and unadjusted mean % changes with corresponding SE and 95% CI per treatment arm will be provided. The difference in LSMEANS and corresponding 90% and 95% CIs will be provided for the difference between the 2 combined active arms and the placebo arm and for the difference between the individual active arms and the placebo arm at the different time points.
 
[REDACTED]
 
[REDACTED]
 
Nominal p-values will be provided for the difference between the 2 combined active arms and the placebo arm and for the difference between the individual active arms and the placebo arm at Week 16. No adjustment for multiplicity will be applied. If warranted, transformations will be considered.
 
[REDACTED]
 
[REDACTED]
 
[REDACTED]
 
Additional sensitivity analyses of the primary endpoint, including the handling of intercurrent events, may be defined in the statistical analysis plan.

Secondary	
Continuous secondary efficacy endpoints will be analyzed similarly to the primary efficacy endpoint using a longitudinal repeated measures model.
 
For the binary secondary efficacy endpoints (e.g., CLASI-50 response) a logistic regression analysis at Week 16 will be provided on the randomized population.
 
[REDACTED]
 
The estimated odds ratio of the 2 combined active arms versus the placebo arm and of the individual active arms versus the placebo arm with the corresponding 2-sided 90% CI and 95% CI will be presented. In addition, the estimated treatment differences and corresponding 90% CI and 95% CI will be provided for the difference in response rate between the 2 combined active arms and the placebo arm and for the difference in response rate between the individual active arms and the placebo arm at the different time points.
 
The handling of missing values and intercurrent events will be described in the SAP. No adjustments for multiplicity will be done for the secondary endpoints.
 
Nominal p-values will be provided for the Week 16 timepoint.
 
[REDACTED]

Abbreviations: CI = confidence interval; CLASI-50 = 50% improvement from baseline in CLASI-A score; CLASI-A = cutaneous lupus erythematosus disease area and severity index activity; LSMEANS = adjusted mean % changes;

[figure not shown]
[REDACTED] SAP = statistical analysis plan; [REDACTED]

